6.4.2 MANAGEMENT OF PAIN DUE TO ELECTROPORATION (EP) PROCEDURES

In case of pain, subjects may be treated with a non-narcotic analgesic (e.g., acetaminophen) after injection/EP.

Medication taken for pain management will be documented as concomitant medications.

6.4.3 ASSESSMENT OF LABORATORY ABNORMALITIES

In Phase 2, samples will be collected for serum chemistry, hematology, and urinalysis at the visits listed in the Schedule of Events (Tables 3 and 4) and as listed in Section 6.4.

Laboratory AEs will be assessed and graded in accordance with the Common Terminology Criteria for Adverse Events (CTCAE), version 5.0. Laboratory values that are not clinically significant (NCS) in the Investigator's opinion will not be reported as AEs.

6.4.4 ASSESSMENT OF CLINICAL TRIAL ADVERSE EVENTS (AES)

Subjects will be queried regarding the occurrence of any AEs including AEs related to injection site reactions, concomitant medications and new onset illness or disease during their study visits and phone calls. Subjects will be reminded to contact study personnel and immediately report any event for the duration of the study. All AEs will be captured from the time of the informed consent until 28 days post-dose 2 (Day 56). Following the Day 56 visit, only SAEs, AESIs and MAAEs will be collected. All related AEs, AESIs and SAEs will be followed to resolution or stabilization. These events will be recorded on the subject's CRF.

6.4.5 ASSESSMENT OF INJECTION SITE REACTIONS

Reactions arising from the IP administration procedure may be reported as administration site or injection site reactions. When evaluating administration (injection) site reactions throughout the study, it is most important to be as specific as possible by selecting the most appropriate term (see Table 10 below) and using the grading scale as listed in the Toxicity Grading Scale for Healthy Adult and Adolescent Volunteers Enrolled in Preventive Vaccine Clinical Trials, issued September 2007. All subjects will be observed for 30

INO-4800	COVID19-311
Inovio Pharmaceuticals, Inc.	Clinical Protocol

minutes following the IP administration procedure for immediate AEs. In addition, other events associated with administration (injection) site reactions (e.g., hematoma, infection or necrosis) should also be reported with preferred terms specific for administration (injection) site reactions.

Local Reaction to Injectable Product (Grade)	Mild (1)	Moderate (2)	Severe (3)	Potentially Life Threatening (4)
Pain	Does not interfere with activity	Repeated use of non- narcotic pain reliever >24 hours or interferes with activity	Any use of narcotic pain reliever or prevents daily activity	Emergency room visit or hospitalization
Tenderness	Mild discomfort to touch	Discomfort with movement	Significant discomfort at rest	ER visit or hospitalization
Erythema/Redness ^a	2.5-5 cm	5.1-10 cm	>10 cm	Necrosis or exfoliative dermatitis
Induration/Swelling ^b	2.5-5 cm and no interference w/ activity	5.1-10 cm or interferes with activity	>10 cm or prevents daily activity	Necrosis

 Table 10: Grading Scale for Injection Site Reactions

September 2007 "FDA Guidance for Industry-Toxicity Grading Scale for Healthy Adult and Adolescent Volunteers Enrolled in Preventive Vaccine Clinical Trials"

^a In addition to grading the measured local reaction at the greatest single diameter, the measurement should be recorded as a continuous variable

^b Should be evaluated and graded using the functional scale as well as the actual measurement.

6.4.6 **CONCOMITANT MEDICATIONS/TREATMENTS**

All medications (prescription and nonprescription), including receipt of any non-study COVID-19 vaccine (authorized under emergency use or licensed) received between informed consent and study discharge (see Section 4.2) must be recorded on the CRFs.

Actual or estimated start and stop dates must be provided. This information will be obtained from the subject and/or any available medical records. The indication for the medication, dose, and dose regimen will be documented.

Therapy considered necessary for the subject's welfare may be given at the discretion of the Investigator or medical provider. If the permissibility of a specific medication/treatment is in question, please contact the Medical Monitor.

The decision to administer a prohibited medication/treatment (Section 6.4.7) is made with the safety of the clinical trial subject as the primary consideration. When possible, the Sponsor should be notified before the prohibited medication/treatment is administered.

6.4.7 **RESTRICTIONS**

In the Phase 2 segment of the trial, subjects should refrain from becoming pregnant until 3 months following the last dose of investigational product by using appropriate

INO-4800	COVID19-311
Inovio Pharmaceuticals, Inc.	Clinical Protocol

contraceptive measures (see Section 4.1.1). In the Phase 3 segment of the trial, subjects should refrain from becoming pregnant until receipt of the last dose of investigation product by using appropriate contraceptive measures (See Section 4.1).

Subjects must not receive any non-study related vaccine (e.g., influenza vaccine) within 2 weeks prior to the first dose of IP, or within 2 weeks of (before or after) any subsequent dose of IP.

Subjects must not have fever (oral temperature \geq 38.0 degrees Celsius or 100.4° Fahrenheit) within 72 hours prior to each dosing.

Subjects should not receive hydroxychloroquine during the trial. In the Phase 3 segment, subjects should not receive any other drug/vaccine intended as COVID-19 prophylaxis during the trial.

For subjects in the Phase 2 segment of the trial, the receipt of any non-study prophylactic COVID-19 vaccine (authorized under emergency use or licensed) is no longer restricted, based upon increasing availability of EUA vaccine and completion of the Phase 2 data for purposes of Phase 3 dose selection.

If a subject informs the site of their intent to receive a non-study prophylactic COVID-19 vaccine (available either under emergency use or when licensed), the subject should be informed that the safety and effectiveness of receiving INO-4800 followed by receipt of another COVID-19 vaccine has not been studied.

Subjects should not participate in any other interventional trials for the duration of this trial.

Subjects must not receive disease modifying doses of anti-rheumatic drugs (e.g., azathioprine, cyclophosphamide, cyclosporine, methotrexate), biologic disease modifying drugs such as TNF- α inhibitors (e.g., infliximab, adalimumab or etanercept) and long term use (\geq 7 days) of oral or parenteral glucocorticoids at a dose of \geq 20 mg/day of prednisone equivalent (use of inhaled, topical, nasal, otic, and ophthalmic corticosteroids are allowed).

6.4.8 SARS-CoV-2 TESTING

Phase 2 segment:

SARS-CoV-2 antibody and RT-PCR testing will be used during screening to test for previous or current SARS-CoV-2 infection. During the trial, subjects who report symptoms suggestive of COVID-19 will be assessed at a COVID-19 assessment visit in the clinic or subject's vehicle or at the subject's home. During this visit, nasal swabs and saliva will be collected to detect SARS-CoV-2 using the RT-PCR assay. Genotyping may also be performed. If the subject is confirmed to be COVID-19 positive, a follow-up nasal swab and saliva will be collected to detect SARS-CoV-2 using the RT-PCR assay at the COVID-19 convalescent visit.

Phase 3 segment:

SARS-CoV-2 antibody testing for Spike protein antibodies will be performed via rapid test in the clinic during screening to identify previous SARS-CoV-2 infection. Serum samples will be collected prior to dosing at Day 0 and at each subsequent visit (see Table 4: Schedule of Events) and tested for nucleoprotein antibodies at the study-designated lab to identify any intervening SARS-CoV-2 infection that may occur, regardless of symptoms, between study visits.

SARS-CoV-2 RT-PCR testing will be conducted on nasopharyngeal specimens collected at Day 0. The Day 0 SARS-CoV-2 RT-PCR results will not be required prior to dosing on that day.

INO-4800	COVID19-311
Inovio Pharmaceuticals, Inc.	Clinical Protocol

A subject should be evaluated at a COVID-19 assessment visit if:

- The SARS-CoV-2 serum antibody test by the study-designated lab (Nucleocapsid protein antibody assay) result becomes positive in subjects who tested seronegative at Day 0 (nucleoprotein antibody assay), with the exception of subjects who have a positive SARS-CoV-2 RT-PCR test result pre-dose on Day 0, or
- A SARS-CoV-2 RT-PCR test result or results of any local rapid testing outside of the study are positive any time after the subject receives the first dose at Day 0, or
- The subject has symptoms of COVID-19 (see Section 6.4.9).

During that COVID-19 Assessment Visit, which may be conducted in the clinic, from the subject's vehicle, or in the subject's home, nasopharyngeal swabs will be collected to detect SARS-CoV-2 using the RT-PCR assay. Genotyping may also be performed on the sample(s) collected at the COVID-19 assessment visit.

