9.3	.2 Compliance with Institutional Review Board (IRB)/Research Ethics Board (REB)/Ethics Committee (EC) Requirements	84
9.3	.3 Compliance with Good Clinical Practice	84
9.3	.4 Compliance with Electronic Records/Signatures Regulations (21CFR Part 11)	84
9.3	.5 Compliance with Protocol	84
9.3	.6 Changes to the Protocol	84
10.0	Data Collection, Monitoring and Reporting	85
10.1	Confidentiality and Privacy	85
11.0	Source Documents	85
11.1	Records Retention	85
12.0	Safety and Quality Monitoring	86
12.1	Safety Review	86
12.2	Clinical Monitoring	86
13.0	Financing and Insurance	87
14.0	Publication Policy	87
15.0	List of Abbreviations	88
16.0	References	90
17.0	Appendices	94
17.1	APPENDIX A: Adverse Events of Special Interest	94

CLINICAL PROTOCOL SYNOPSIS

Protocol Title: Phase 2/3 Randomized, Blinded, Placebo-Controlled Trial to Evaluate the Safety, Immunogenicity, and Efficacy of INO-4800, a Prophylactic Vaccine against COVID-19 Disease, Administered Intradermally Followed by Electroporation in Adults at High Risk of SARS-CoV-2 Exposure

Protocol Number: COVID19-311

Clinical Trial Phase: 2/3

Estimated Number of Clinical Trial Centers and Countries/Regions: Approximately 70-100 centers in Latin America, Asia Pacific, North America and Africa.

Background:

INO-4800 is a prophylactic vaccine under development against SARS-CoV-2, the causative agent of COVID-19. INO-4800 contains the plasmid pGX9501, which encodes for the full length of the Spike glycoprotein of SARS-CoV-2. The goal of this trial is to assess the safety, immunogenicity and efficacy of INO-4800 to prevent COVID-19 in subjects at high risk of exposure to SARS-CoV-2.

Clinical Trial Design:

This is an operationally seamless Phase 2/3, randomized, placebo-controlled, multi-center trial to evaluate the safety, immunogenicity, and efficacy of INO-4800, administered by intradermal (ID) injection followed immediately by electroporation (EP) using the CELLECTRA[®] 2000 device, in a 2-dose regimen (Days 0 and 28) in adults who are at high risk of SARS-CoV-2 exposure. The primary objectives of this trial are to identify in seronegative subjects an optimal age-related dose of INO-4800 in the Phase 2 segment for a subsequent efficacy evaluation in the Phase 3 segment.

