b. Full physical examination only at Screening and Day 393 (or EOS). Targeted physical exam at other indicated visits.

INO-4800 Inovio Pharmaceuticals, Inc.

- c. In women of childbearing potential. Urine pregnancy test at all indicated visits.
- d. Intradermal injection(s) in skin preferably over deltoid region, or alternately over anterolateral quadriceps region, followed by EP at Day 0 and Day 28.
- e. Following administration of INO-4800 or placebo, a subset of sites will be required to download EP data from the CELLECTRA® 2000 device and provided to Inovio.
- f. AEs to be collected from time of consent to Day 56; SAEs, MAAEs, and AESIs to be collected from time of consent to EOS.
- g. On Day 0, cellular sampling requires 64 mL of whole blood prior to 1st dose. At all other time points, collect 32 mL of whole blood. Cellular samples will be collected at selected clinical sites (estimated to include 711 subjects)
- h. On Day 0, humoral sampling requires a total of 17 mL of whole blood (two 10-mL red top serum collection tubes, each 8.5 mL of whole blood, to produce four serum aliquots of 2 mL each). At all other time points, collect 8.5 mL of whole blood in a single 10-mL red top serum collection tube to produce two serum aliquots of 2 mL each.
- i. SARS-CoV-2 antibody. Screening samples will be tested in the clinic via rapid test to detect antibodies against the Spike protein. Samples collected pre-dose Day 0 and at subsequent timepoints will be tested at a study-designated lab to detect antibodies against the Nucleocapsid protein.
- j. The Day 0 RT-PCR results will not be required prior to dosing on that day.
- k. Day 42 visit must occur at least 10 days after Day 28 visit.
- I. Subjects will be evaluated during a "COVID-19 assessment visit" when acute COVID-19 is suspected. The assessment visit may be performed in the clinic, subject's vehicle, or at a home visit and should be completed within 3 days of symptom onset or within 3 days of a positive result of a SARS-CoV-2 test.
- m. For subjects with virologically-confirmed SARS-CoV-2 infection during the trial, a convalescent visit should be scheduled approximately 28 days after symptom onset, or in the absence of symptoms, after the collection date of any specimen testing positive for SARS-CoV-2 RT-PCR. If acute symptoms are ongoing the site should follow up with the subject via phone call or unscheduled visit after symptom resolution or stabilization

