1.3.5 FIRST-IN-HUMAN PHASE 1 TRIAL OF INO-4800

In the open-label, Phase 1 clinical trial, we initially evaluated the safety and immunogenicity of INO-4800 in 40 healthy participants, 18-50 years of age. There were two groups of 20 participants each who received either 1.0 mg or 2.0 mg of INO-4800 intradermally followed by EP at 0 and 4 weeks. In the first 40 subjects, by Week 8, 11

INO-4800	COVID19-311
Inovio Pharmaceuticals, Inc.	Clinical Protocol

adverse events were reported of which all were Grade 1 in severity of which 6 were related to study drug. The frequency of AEs did not increase with the second administration.

From the immunogenicity analysis of the initial 40 subjects enrolled, two subjects were excluded from the analysis, one due to early discontinuation prior to the Week 4 dose for non-study reasons and the other due to suspected exposure to SARS-CoV-2 before the first dose of INO-4800 was administered based on a baseline positive SARS-CoV-2 serology. Thirty-eight (38) evaluable subjects had cellular and/or humoral immune responses following the second dose of INO-4800. Assessment of data from both Week 6 and Week 8 ELISpot revealed that 74% and 100% of the subjects generated T cell responses in the 1.0 mg and 2.0 mg groups, respectively. By Week 6, 95% (36 of 38) of the participants seroconverted by generating binding and/or neutralizing antibodies. Overall, INO-4800 elicited antigen-specific humoral and cellular immune responses against the SARS-CoV-2 Spike protein while demonstrating favorable safety and tolerability.

The protocol was amended to include an additional 80 healthy participants to evaluate safety and immunogenicity of INO-4800 in older and elderly age populations. A lower dose level (0.5 mg) was also added for evaluation of dose-sparing potential. A total of 40 participants were enrolled into three dose levels (0.5 mg, 1.0 mg and 2.0 mg), such that each Group included 20 participants 18-50 years of age, 10 participants 51-64 years of age, and 10 participants 65 years of age and older. Doses were delivered intradermally followed by EP at 0 and 4 weeks. As of March 10, 2021, 35 related adverse events were reported cumulatively, of which all but three (Grade 2 injection site pruritus, lethargy and abdominal pain) were Grade 1 in severity.

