3.7 EFFICACY ASSESSMENT (PHASE 3 SEGMENT ONLY)

Subjects will receive either active investigational product (INO-4800, dose selected from the Phase 2 segment) or placebo in a 2-dose regimen administered intradermally followed immediately by EP on Days 0 and 28. Subjects will be monitored through regularly scheduled clinic visits and phone calls throughout the trial. Subjects will be regularly tested for SARS-CoV-2 infection using serologic testing. If COVID-19 disease (including severe COVID-19) is suspected based on symptoms or laboratory testing, site personnel will arrange for a clinic visit. Subjects with symptom(s) or a positive SARS-CoV-2 test result will be reviewed by the independent blinded EAC. The EAC will adjudicate all suspected COVID-19 events and determine whether cases meet the case definitions for COVID-19 disease, severe COVID-19 or SARS-CoV-2 asymptomatic infection.

The mechanism for review and confirmation of cases will be outlined in an EAC Charter.

3.7.1 CASE DEFINITION FOR VIROLOGICALLY-CONFIRMED COVID-19 DISEASE:

- Positive testing by SARS-CoV-2 RT-PCR assay (performed at central lab*) with fever (temperature of 100.4°F/38.0°C or higher), or
- Positive testing by SARS-CoV-2 RT-PCR assay (performed at central lab*) with any of the following COVID-19 related symptoms:
 - Feeling feverish or chills
 - Cough
 - Shortness of breath or difficulty breathing
 - Fatigue
 - Muscle or body aches
 - Headache
 - New loss of taste or smell
 - Sore throat
 - Congestion or runny nose
 - Nausea or vomiting
 - Diarrhea

*Local lab results will be accepted if the subject is hospitalized and a sample is not able to be obtained for analysis at central lab.

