Urine samples will be tested by dipstick for glucose, protein, and hematuria at Screening (Phase 2 segment only) and at visits specified in the Schedule of Events (Tables 3 and 4). If abnormal (presence of protein, hematuria, or glucose \geq 1+), a microscopic examination should be performed.

INO-4800	COVID19-311
Inovio Pharmaceuticals, Inc.	Clinical Protocol

Serology:

HIV antibody or rapid test will be performed at Day 0 only.

Antibodies to SARS-CoV-2 will be measured at Screening in the clinic using a rapid test which detects Spike protein antibodies and at pre-dose Day 0 and subsequent visits via testing at a study-designated lab which detects antibodies to Nucleocapsid protein. Timepoints are specified in the Schedule of Events (Tables 3 and 4).

Pregnancy Testing:

Pregnancy testing will be performed on women of childbearing potential (WOCBP). All women will be assumed to be of childbearing potential unless they are:

- Women who are post-menopausal as defined by reported spontaneous amenorrhea for ≥ 12 months;
- Women who are surgically sterile or have a partner who is sterile (i.e., vasectomy in males or tubal ligation, absence of ovaries and/or uterus in females). In the case of a vasectomy, subjects should wait six (6) months post-vasectomy to be considered sterile.

Phase 2: For WOCBP, a serum pregnancy test will be obtained at Screening and a urine pregnancy test will be performed immediately prior to any dosing and at the subject's last visit.

Phase 3: For WOCBP, a urine pregnancy test will be obtained at Screening and will be performed immediately prior to any dosing.

A negative result for urine β -HCG (test must have a sensitivity of at least 25 mlU/mL) must be available prior to each administration of IP. If the β -HCG test is positive, indicating that the subject is pregnant prior to completing the specified dose regimen, then no further IP will be administered. Every attempt should be made to follow pregnant subjects for the remainder of the study and to determine the outcome of the pregnancy (see Section 7.12).

DIARY

Diaries will be implemented in the Phase 2 segment of the protocol and at selected sites (estimated to include 711 subjects) in the Phase 3 segment. Subjects will be provided a diary to record the following solicited local and systemic AEs:

- Oral temperature and time taken (each daily entry before 11:59 pm)
- Solicited systemic symptoms
- Solicited local injection site symptoms
- Concomitant medications

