7.11 REPORTING SUSPECTED COVID-19 DISEASE CASES DURING THE TRIAL

For both Phase 2 and Phase 3 segments of the trial, all suspected COVID-19 disease cases based on reported COVID-19 symptoms and/or SARS-CoV-2 test results should be entered into the Suspected COVID-19 Clinical Event CRF within 24 hours of awareness. Cases will be tracked until final determination of whether the case meets criteria of a confirmed COVID-19 disease case, per the case definition. For the Phase 2 segment of the trial, this determination will be made by the Investigator. For the Phase 3 segment, this determination will be made by the EAC.

If the reported COVID-19 disease case is later determined not to be a confirmed COVID-19 case, the event (e.g. symptoms or other diagnosis), if serious, would be reported as an SAE within 24 hours following determination by the Investigator (Phase 2 segment) or notification by EAC (Phase 3 segment).

If the reported COVID-19 disease case is later determined not to be a confirmed COVID-19 case, the event (e.g. symptoms or other diagnosis), if non-serious and if occurring from the time of consent until 28 days post-dose 2, would be reported as an AE following determination by the Investigator (Phase 2 segment) or notification by EAC (Phase 3 segment).

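### The second Phase 3 assessment-visit trigger (Section 6.4.8) does not exclude outside Spike-antibody rapid tests, so vaccination itself can set it off and bring a result suggesting assignment to blinded staff

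*Protocol*

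**What the plan says.** All references are to protocol version 7.0, Phase 3 segment.

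- **Triggers.** Section 6.4.8 lists three reasons for a COVID-19 assessment visit. The first is a newly positive Nucleocapsid antibody result from the study-designated laboratory. The second is a positive RT-PCR, or that "results of any local rapid testing outside of the study are positive any time after the subject receives the first dose at Day 0". The third is symptoms.
- **What the protocol calls a rapid test.** The same section states that "SARS-CoV-2 antibody testing for Spike protein antibodies will be performed via rapid test in the clinic during screening". The serology text of Section 6.4 agrees: "Antibodies to SARS-CoV-2 will be measured at Screening in the clinic using a rapid test which detects Spike protein antibodies".
- **Post-dose study serology.** Table 4, footnote i: "Samples collected pre-dose Day 0 and at subsequent timepoints will be tested at a study-designated lab to detect antibodies against the Nucleocapsid protein". Section 3.7.2 also defines asymptomatic infection by Nucleocapsid antibody.
- **The vaccine.** Synopsis, Background: "INO-4800 contains the plasmid pGX9501, which encodes for the full length of the Spike glycoprotein of SARS-CoV-2".
- **What follows a positive test.** Section 3.7: "Subjects with symptom(s) or a positive SARS-CoV-2 test result will be reviewed by the independent blinded EAC". Section 7.11 says that suspected cases "based on reported COVID-19 symptoms and/or SARS-CoV-2 test results should be entered into the Suspected COVID-19 Clinical Event CRF within 24 hours of awareness".
- **Blinding.** Section 5.2.1 keeps the Sponsor, subjects and site staff other than pharmacy personnel blinded.

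**The concern.** The first trigger is worded so that vaccine-induced antibody cannot set it off: a Spike-only vaccine does not induce Nucleocapsid antibody. The second trigger has no such protection. It accepts any outside rapid test, and the only SARS-CoV-2 test that the protocol itself describes as rapid is one that INO-4800 can be expected to turn positive.

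Two things are at stake. First, the visit brings a nasopharyngeal swab, so vaccinees could be swabbed more often than placebo recipients for a reason unrelated to infection. Second, a positive Spike result with negative Nucleocapsid and PCR results points towards INO-4800, and the visit and reporting rules carry it to people who should remain blinded.

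**Working it through.** The plan gives no figure on this point. The check is therefore mainly a comparison of wording, followed by arithmetic on stated assumptions.

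**1. Does any other text narrow the trigger?** Table 4 footnote l and Sections 6.1.2.7 and 6.4.9 speak of a positive SARS-CoV-2 test without naming the type. Section 6.4.7 (Restrictions) does not address outside antibody testing. Nothing shown tells sites to disregard or mask a post-dose Spike result. The gap is in the current text.

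**2. Is a positive result arm-dependent?** Section 1.3.7.1 gives a binding GMT at the 2.0 mg dose of 93.5 at baseline and 2210.0 at Week 6, with a stated geometric mean fold rise of 23.5. Section 1.3.5 reports for Phase 1: "By Week 6, 95% (36 of 38) of the participants seroconverted by generating binding and/or neutralizing antibodies". That figure pools 1.0 mg and 2.0 mg and counts either kind of antibody. Neither source measures rapid-kit positivity. Together with the Spike antigen, they support the direction of the difference but not a rate.

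**3. How many visits might follow?** The inputs below are assumptions, except the arm sizes of 6,668 and 3,334 seronegative subjects (Phase 3 enrolment table in the synopsis).

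- *u*, share of subjects taking an outside Spike-antibody test: 1% to 10%
- *s*, positivity on INO-4800: 70% to 95%
- *q*, positivity on placebo: 2% to 10%

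Extra visits = arm size × u × positivity.

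| | Low | High |
|---|---|---|
| INO-4800 | 6,668 × 0.01 × 0.70 = 47 | 6,668 × 0.10 × 0.95 = 633 |
| Placebo | 3,334 × 0.01 × 0.02 = 0.7 (about 1) | 3,334 × 0.10 × 0.10 = 33 |

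The more than tenfold width of the INO-4800 range shows how little the document fixes. If Spike-antibody tests are excluded, vaccine-induced positives trigger no visits in either arm.

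**4. How many extra cases?** A vaccine-induced antibody result is unrelated in time to infection, so the extra swab finds only infection present by chance. At an assumed point prevalence of 2%, the swabs on INO-4800 would give 47 × 0.02 = 0.9 to 633 × 0.02 = 12.7 PCR positives. A case also needs fever or a listed symptom (Section 3.7.1), and symptoms already trigger a visit in both arms. Only subjects with unreported symptoms, or with symptoms starting after the swab, would be added.

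**5. How informative is a positive Spike result?** With 2:1 allocation and equal test-taking by arm, P(INO-4800 | positive) = (2/3)s / [(2/3)s + (1/3)q].

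- s = 0.70, q = 0.10: 0.4667 / (0.4667 + 0.0333) = 0.93
- s = 0.95, q = 0.02: 0.6333 / (0.6333 + 0.0067) = 0.99

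The probability before the test is 0.67. If non-study vaccination among placebo recipients raises q towards s, the result falls back to 2/3 and carries no information.

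**6. Primary endpoint.** With k = 0.5, p0 = 0.70/1.20 = 0.583 and p1 = 0.10/0.60 = 0.167. At 17 severe cases the exact test succeeds with at most 5 on INO-4800, and power is 95.0%, which meets the stated 90%. If differential ascertainment inflated severe cases on INO-4800 by 5%, 10% or 25%, power would be 94.0%, 93.0% or 89.4%. Nothing suggests inflation of that order, because severe cases are symptomatic and qualify for a visit in either arm.

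**The case against.** The strongest reply is that the natural reading is benign. Outside rapid testing is paired with RT-PCR, while antibody has its own trigger, limited to Nucleocapsid. The visit is meant for suspected acute disease, which a Spike-antibody result does not indicate. The drafters probably meant antigen tests, and the rule says that a subject should be evaluated, not must. This lowers the likelihood of harm, but the text still says any rapid test, and sites work from the text.

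A reader might also infer more than the document supports:

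- **That such a record identifies an INO-4800 recipient.** It does not. Sections 4.3 and 6.4.6 foresee subjects who receive a non-study COVID-19 vaccine and stay in follow-up, and a placebo recipient could then show the same pattern. Kit false positives are another source.
- **That the EAC will see the Spike result.** Section 3.7 sends positive tests to the EAC but leaves the mechanism to a charter that is not shown.
- **That the trigger is what unblinds.** A subject who takes a private Spike test may be unblinded whatever the trigger says. The trigger adds a route by which the result reaches site staff and trial records.
- **That efficacy estimates are materially distorted.** Symptomatic subjects are swabbed in either arm, endpoints 2a and 2b carry no hypothesis test (Section 8.5.2.1), and the bias would lower apparent efficacy.
- **That the Screening kit shares the defect.** It is scheduled only at Screening and is not outside testing.

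**Conclusion.** The wording gap is real and current. Read literally, one of the three visit triggers can fire because of vaccination, mainly in the INO-4800 arm. It then brings a result suggestive of assignment to blinded site staff and the Suspected COVID-19 CRF, contrary to the protection that the protocol builds in elsewhere by using Nucleocapsid serology.

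Its frequency cannot be estimated from the document, and the counts above only illustrate the mechanism. That vaccinees test positive more often is inferred from the antigen and the laboratory antibody data, not from kit data. The severe primary endpoint is little affected. Any ascertainment bias in 2a and 2b should be small and conservative. The blinding risk is the stronger ground, and it is one of suggestion, not proof. The correction is worth making because it is cheap and completes a safeguard that the protocol already intends.

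**What to change.** 1. In the second trigger of Section 6.4.8, require a positive SARS-CoV-2 RT-PCR, or a positive local rapid antigen or nucleic-acid test taken outside the study.
2. Wherever a positive SARS-CoV-2 test serves as a visit trigger or reporting criterion (Sections 3.7, 6.1.2.7, 6.4.9 and 7.11, and Table 4 footnote l), state that post-dose Spike-antibody results are excluded and that study-laboratory Nucleocapsid seroconversion still counts. Limiting these places to antigen and nucleic-acid tests alone would go too far: it would drop the seroconversions that the first trigger uses and that the EAC needs to adjudicate asymptomatic infection.
3. State that a post-dose Spike-antibody result on its own is not entered in the Suspected COVID-19 CRF or forwarded to the EAC.

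The cost is a few sentences and a line in the CRF completion guidance. It adds no visit or test, and it removes visits triggered only by vaccine-induced antibody. It does not stop a subject from testing privately.
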